## 11. STUDY DRUG

### 11.1 Study Drug Administration

Current protocol-specific criteria for administration of TAK-228 must be met and documented before drug administration. Study drug will be administered only to eligible patients under the supervision of the investigator.

TAK-228 will be administered on an empty stomach. Patients should be instructed to refrain from eating and drinking (except for water and prescribed medications) for 2 hours before and 1 hour after each dose. Patients should drink at least 8 ounces (240 mL) of water with their TAK-228 dose. Patients should be instructed to take their study medication in the morning on each scheduled dosing day (day 1 of each week  $\pm$  1 day) and not to take more than the prescribed dose at any time. Patients should swallow the study medication whole and not chew it, open it, or manipulate it in any way before swallowing. If a patient does not take their TAK-228 dose on the scheduled dosing day (day 1 of each week  $\pm$  1 day), then this will be considered a missed dose. Patients should record any missed doses in their diary and resume drug administration at the next scheduled time with the prescribed dosage. Under no circumstance should a patient repeat a dose or double-up doses.

If severe emesis or mucositis prevents the patient from taking scheduled doses, that dose will be skipped. If emesis occurs after study medication ingestion, the dose will not be readministered, and patients should resume dosing at the next scheduled time with the prescribed dosage. Patients should record the occurrence of the emesis in their dosing diaries. Under no circumstance should a patient repeat a dose or double-up doses.

Tamoxifen will be administered by the patient pursuant of a prescription obtained from the patient's pharmacy. It is to be administered with or without food QD. Patients should be instructed to take their tamoxifen at approximately the same time each day and not to take more than the prescribed dose at any time. On TAK-228 scheduled dosing days, tamoxifen should be taken in the evening (before bed). Patients should swallow the tamoxifen whole and not chew it, crush it, or manipulate it in any way before swallowing.

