#### 11.1.1 Dose Modification Guidelines

TAK-228 should be administered, unless the patient has a grade 3 or greater TAK-228-related event. Guidelines for dose interruption and dose reduction are described below.

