#### 11.1.2 Criteria for Dose Interruption During a Cycle/Visit

TAK-228 should be withheld for treatment-related toxicities that are grade 3 or higher despite supportive treatment per standard clinical practice. If the event resolves to grade 1 (or grade 2 for hyperglycemia or rash) or to baseline values within 3 weeks of interrupting treatment, then the patient may resume study treatment at a dose level reduced by 1 level.

The following non-hematologic toxicities attributed to TAK-228 would not require dose interruption:

- Grade 3 or higher nausea and/or emesis in the absence of optimal antiemetic prophylaxis (optimal antiemetic prophylaxis is defined as an antiemetic regimen that employs both a serotonin type 3 receptor antagonist and a corticosteroid given in standard doses and according to standard schedules)
- Grade 3 or higher diarrhea that occurs in the absence of optimal supportive therapy
- Grade 3 fatigue

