## 11.6 Management of Clinical Events

### 11.6.1 Management of Hyperglycemia

Based on the TAK-228 clinical trials, most hyperglycemia episodes occurred within the first 60 days after initiation of treatment with TAK-228 and have been grade 1 or 2 and have responded quickly to oral metformin. Hyperglycemia has not been dose-limiting since instituting a standard regimen for early treatment of hyperglycemia.

All patients who develop hyperglycemia during the study should have their glucose closely monitored by study staff. The investigator may choose either to continue close monitoring of patients who develop grade 1 hyperglycemia ( $FSG > ULN \leq 160$  mg/dL) or, alternatively, consider initiating treatment with an oral hypoglycemic agent, such as metformin. All patients with grade  $\geq 2$  hyperglycemia ( $FSG > 160$  mg/dL) must be treated aggressively with oral hypoglycemic agents and/or insulin as clinically indicated while continuing on TAK-228. The investigator should consult an endocrinologist, if needed, to aid in optimizing the patient's hyperglycemia treatment plan.

It is recommended that patients be treated initially with a fast-acting insulin sensitizer, such as metformin, at 500 mg p.o. QD and titrate up to a maximum of 1000 mg p.o. twice daily as needed. Concurrent administration of dipeptidyl peptidase-4 inhibitors (e.g., sitagliptin or vildagliptin) and/or insulin should also be considered. Oral sulfonylureas (e.g., glipizide or glyburide) should be used with caution due to the higher hypoglycemia risk. The dose of oral hypoglycemic agents should be adjusted in patients with renal insufficiency. Hyperglycemic patients should also be encouraged to follow a low carbohydrate diet.

If any fasting serum glucose reading performed at the site indicates hyperglycemia ( $> ULN$  or  $\geq 110$  mg/dL), the study staff should first ascertain that the patient was fasting at the time of the blood draw (i.e., nothing by mouth for at least 8 hours prior to blood being obtained).

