### In-Home Daily Fasting Glucose Monitoring

In addition to obtaining fasting glucose levels at the clinic visits as outlined in the Schedule of Events, all patients will be given a glucometer to monitor their daily FBG levels at home. The level should be collected daily, predose on dosing days, and at approximately the same time each day.

On Cycle 1 Day 1, the patient will be provided an in-home glucometer. Patients will be trained on proper use of the glucometer and instructed to collect a daily FBG level every morning (predose on dosing days), starting on Cycle 1 Day 2. Patients will be instructed to bring the glucometer with them to each study visit so that the data collected can be reviewed and recorded in the source documents. Investigators will be responsible for reviewing the home glucose monitoring logs for hyperglycemia.

The patient will be instructed to contact the site immediately if the value is abnormal (i.e.,  $\geq 150$  mg/dL) for further instructions on the management of their hyperglycemia. Hyperglycemia observed during home glucose monitoring should be confirmed in the clinic.

If no irregularities in the fasting blood glucose level are observed during a minimum of 2 consecutive months, then the frequency of in-home fasting blood glucose testing can be reduced to a minimum frequency of once weekly, depending on the investigator's judgment and approval. Patients will continue to notify the investigator of fasting blood glucose levels that exceed 150 mg/dL and, if blood glucose levels are not well controlled, or if the patient requires either oral hypoglycemic agents or insulin to control blood glucose levels, then the frequency of in-home testing of FBG levels will be reinstated to daily.

Guidance on TAK-228 dose modification for patients with hyperglycemia is provided in Table 8 below.

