**TABLE 8 MANAGEMENT OF HYPERGLYCEMIA**

Grade	Description	Treatment	Dose Modification
1	Fasting blood sugar >ULN to 160 mg/dL	
 
Continue close monitoring of blood sugar.
 
Initiate oral hypoglycemic agent.
 
	None
2	>160 to 250 mg/dL	
 
Initiate oral hypoglycemic agent and/or insulin if not well controlled on oral agent.
 
	None
≥3	>250 mg/dL	
 
Initiate oral hypoglycemic agent and/or insulin.
 
	Hold TAK-228 until ≤grade 2. Resume TAK-228 based on timing of recovery after maximal treatment: 
 
≤1 week: resume TAK-228 at same dose and schedule.
 
>1 but ≤2 weeks: reduce TAK-228 by 1 dose level
 
>2 weeks: discontinue patient from the study.
 

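### Section 11.6.1 keeps all grade ≥2 hyperglycemia on TAK-228 with no upper limit, while Table 8 in the same section holds the drug at grade ≥3; the narrative clause should be confined to grade 2

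*Combined protocol and SAP*

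**What the plan says.** The management narrative in section 11.6.1 separates grade 1 from everything above it. At grade 1 the investigator may monitor or start an oral agent. All patients at grade 2 or higher, defined only as fasting serum glucose (FSG) above 160 mg/dL, "must be treated aggressively with oral hypoglycemic agents and/or insulin as clinically indicated while continuing on TAK-228".

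Table 8, which closes the dosing guidance in the same section, splits that range. Grade 2 is above 160 to 250 mg/dL, with no dose modification. Grade 3 or higher is above 250 mg/dL, with the instruction "Hold TAK-228 until ≤grade 2". What follows depends on how long recovery takes after maximal treatment: up to 1 week, same dose and schedule; more than 1 and up to 2 weeks, one dose level lower; more than 2 weeks, "discontinue patient from the study".

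Other relevant text:

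- In-home monitoring part of 11.6.1: "Guidance on TAK-228 dose modification for patients with hyperglycemia is provided in Table 8 below".
- Section 11.1: "Current protocol-specific criteria for administration of TAK-228 must be met and documented before drug administration".
- Section 11.1.1: "TAK-228 should be administered, unless the patient has a grade 3 or greater TAK-228-related event".
- Section 11.1.2: "TAK-228 should be withheld for treatment-related toxicities that are grade 3 or higher despite supportive treatment per standard clinical practice". It sets a recovery threshold of grade 2 for hyperglycemia and does not list hyperglycemia among the toxicities exempt from interruption.
- Section 4.1.1 gives the same treatment instruction for grade 2 or higher, without the words about continuing TAK-228.

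**The concern.** Grade 2 or higher includes grades 3 and 4. Read as written, the narrative sentence keeps a patient above 250 mg/dL on TAK-228, while the table a page later withholds the drug from the same patient. Hyperglycemia is a known toxicity of this drug class, and this is the rule for its most severe form.

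The question is practical. Patients must report home readings of 150 mg/dL or more to the site at once, and fasting glucose is measured before the dose on TAK-228 dosing days (Table 1, footnote g). Site staff will therefore usually have a value in hand and turn to section 11.6.1, where they find two different dosing instructions and no statement of which prevails. The frequencies of dose interruption, reduction and discontinuation reported under section 13.1.8 would then depend on which text was followed.

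**Working it through.** The protocol states no figure on this point to reproduce. The check is a side-by-side reading by glucose band.

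| Fasting glucose | Grade | Narrative, 11.6.1 | Table 8 | Agree? |
|---|---|---|---|---|
| >160 to 250 mg/dL | 2 | Treat, continue TAK-228 | Treat, no dose modification | Yes |
| >250 mg/dL | ≥3 | Treat, continue TAK-228 | Treat, hold TAK-228; then resume, reduce or discontinue | No |

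**Does other text limit the narrative sentence?**

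1. The pointer in 11.6.1 sends dose modification to Table 8. It calls the table guidance, whereas the narrative says patients must be treated while continuing. It does not say that the table overrides the narrative.
2. Section 11.1 requires administration criteria to be met before dosing, but does not say which of two conflicting criteria applies.
3. Section 11.1.1 excepts grade 3 or greater events from dosing, but only those related to TAK-228.
4. Section 11.1.2 withholds the drug only for treatment-related toxicity that is grade 3 or higher despite supportive treatment. An investigator who starts insulin and gives the next dose could cite both this condition and the narrative. Table 8's hold carries no such condition.
5. Section 4.1.1 is silent on continuing.

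All five are compatible with holding at grade 3 or higher, and items 1, 3 and 4 point clearly to it. None confines the clause in 11.6.1 to grade 2.

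**What differs for one patient.** TAK-228 is given once weekly for 16 weeks, so the planned total at the starting dose is 16 × 30 mg = 480 mg. If glucose rises above 250 mg/dL and recovers between two dosing days, neither text costs a dose. If it is still above 250 mg/dL when a dose is due, the narrative gives that dose and Table 8 withholds it. Each dose held at 30 mg is 30/480 = 6.25% of the planned total. A one-level reduction then lowers later doses from 30 to 20 mg (Table 7).

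The total loss under Table 8 cannot be fixed from the documents. The table counts recovery after maximal treatment, and the time needed to reach maximal treatment is not stated. Section 11.6.1 has metformin titrated from 500 mg daily up to 1000 mg twice daily, with other agents considered, so maximal treatment may come some time after onset.

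**How many patients.** The documents give no rate of grade 3 or higher hyperglycemia on TAK-228. Section 11.6.1 says that most episodes were grade 1 or 2, and entry requires FSG of at most 130 mg/dL (section 10.1, criterion 7d). Few cases are expected, but no number follows.

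**The case against.** The strongest reply is that the section, read as a whole, gives one answer. It assigns dose modification to Table 8, and sections 11.1.1 and 11.1.2 stop dosing at grade 3. On this view the narrative sentence concerns glucose-lowering therapy, and its closing phrase means only that hyperglycemia should be treated rather than used as a reason to take the patient off the drug. That fits the statement in the same section that hyperglycemia has not been dose-limiting since early treatment became standard. It also fits the Table 8 branch in which a patient who recovers within a week resumes at the same dose.

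Much of this stands. The intent is to hold, and most investigators would probably follow the table. What does not stand is that the text settles the matter. The sentence covers all grades from 2 upward and is phrased as mandatory. Even if continuing means only not discontinuing, it conflicts with Table 8, which discontinues the patient when recovery takes more than 2 weeks. That step comes later in management, but the narrative makes no exception for it.

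A reader might infer more: that the protocol deliberately doses through severe hyperglycemia, or that the discrepancy materially changes exposure or the efficacy result. The documents do not support either reading. Table 8 and sections 11.1.1 and 11.1.2 contradict the first. For the second, there is no grade ≥3 rate and no ground for expecting sites to disregard the table.

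**Conclusion.** The inconsistency is real and lies in the current operative text. It is minor, and it is a wording conflict in a safety rule rather than a questionable design choice. Its reach is limited to patients above 250 mg/dL when a weekly dose is due, and to the descriptive safety counts in section 13.1.8. The Ki67 analysis and sample size do not use this rule, and the accrual-suspension rule in section 13.1 defines its event as progression within 16 weeks.

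The textual conclusion rests on no numerical assumption. The statement that few patients are affected rests on the protocol's description of past episodes and on the entry limit for glucose. It is not an estimate.

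**What to change.** In section 11.6.1, restrict the clause about continuing TAK-228 to grade 2 (FSG >160 to 250 mg/dL), and add:

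*For grade ≥3 (>250 mg/dL), treat with oral hypoglycemic agents and/or insulin; TAK-228 is held, and resumed, reduced or discontinued per Table 8, which governs dose modification for hyperglycemia.*

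This keeps the duty to treat grade 3 or higher and changes only the dosing instruction. Naming Table 8 as governing also settles a neighboring difference: section 11.1.2 allows up to 3 weeks for recovery and then a one-level reduction, whereas Table 8 resumes the same dose within 1 week and discontinues after 2.

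The cost is one edited and one added sentence. Table 8, the design, the sample size and the analysis stay as they are.

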### In-Home Daily Fasting Glucose Monitoring

In addition to obtaining fasting glucose levels at the clinic visits as outlined in the Schedule of Events, all patients will be given a glucometer to monitor their daily FBG levels at home. The level should be collected daily, predose on dosing days, and at approximately the same time each day.

On Cycle 1 Day 1, the patient will be provided an in-home glucometer. Patients will be trained on proper use of the glucometer and instructed to collect a daily FBG level every morning (predose on dosing days), starting on Cycle 1 Day 2. Patients will be instructed to bring the glucometer with them to each study visit so that the data collected can be reviewed and recorded in the source documents. Investigators will be responsible for reviewing the home glucose monitoring logs for hyperglycemia.

The patient will be instructed to contact the site immediately if the value is abnormal (i.e.,  $\geq 150$  mg/dL) for further instructions on the management of their hyperglycemia. Hyperglycemia observed during home glucose monitoring should be confirmed in the clinic.

If no irregularities in the fasting blood glucose level are observed during a minimum of 2 consecutive months, then the frequency of in-home fasting blood glucose testing can be reduced to a minimum frequency of once weekly, depending on the investigator's judgment and approval. Patients will continue to notify the investigator of fasting blood glucose levels that exceed 150 mg/dL and, if blood glucose levels are not well controlled, or if the patient requires either oral hypoglycemic agents or insulin to control blood glucose levels, then the frequency of in-home testing of FBG levels will be reinstated to daily.

Guidance on TAK-228 dose modification for patients with hyperglycemia is provided in Table 8 below.

**TABLE 8 MANAGEMENT OF HYPERGLYCEMIA**

Grade	Description	Treatment	Dose Modification
1	Fasting blood sugar >ULN to 160 mg/dL	
 
Continue close monitoring of blood sugar.
 
Initiate oral hypoglycemic agent.
 
	None
2	>160 to 250 mg/dL	
 
Initiate oral hypoglycemic agent and/or insulin if not well controlled on oral agent.
 
	None
≥3	>250 mg/dL	
 
Initiate oral hypoglycemic agent and/or insulin.
 
	Hold TAK-228 until ≤grade 2. Resume TAK-228 based on timing of recovery after maximal treatment: 
 
≤1 week: resume TAK-228 at same dose and schedule.
 
>1 but ≤2 weeks: reduce TAK-228 by 1 dose level
 
>2 weeks: discontinue patient from the study.
 

**Prevention/Prophylaxis:**

- Follow fasting glucose levels during clinic visits.
- Monitor home glucometer test results.
- Check HbA1c levels every 3 months during therapy.
- Recommend life-style modifications, as appropriate (balanced diet, limited alcohol consumption, increased physical activity).
- Most episodes of grade 1 or 2 hyperglycemia respond quickly to oral metformin. Early initiation of therapy at the lowest therapeutic dose is recommended to prevent higher grade hyperglycemia.
- Fasting blood glucose levels ≥150 mg/dL by glucometer should be followed by closer monitoring of serum glucose and possible intervention.

HbA1c=glycosylated hemoglobin; ULN=upper limit of normal.

### 11.6.2 Management of Hyperlipidemia

Guidance on TAK-228 dose modification for patients with hyperlipidemia is provided in Table 9.

**TABLE 9 MANAGEMENT OF HYPERLIPIDEMIA**

Grade	Description	Treatment	Dose Modification
1	Cholesterol >ULN to 300 mg/dL Triglycerides >150 to 300 mg/dL	None	None
2	Cholesterol >300 to 400 mg/dL Triglycerides >300 to 500 mg/dL	
 
Treat hyperlipidemia according to standard guidelines.
 
Triglycerides ≥500 mg/dL should be treated urgently, due to risk of pancreatitis.
 
	
 
Maintain dose, if tolerable.
 
If toxicity becomes intolerable, interrupt TAK-228 until recovery to ≤grade 1. Re-initiate TAK-228 at the same dose level.
 

3	Cholesterol >400 to 500 mg/dL Triglycerides >500 to 1000 mg/dL	Same as for grade 2.	Hold TAK-228 until recovery to ≤grade 1, then reinitiate TAK-228 at a dose reduced by 1 level.
4	Cholesterol >500 mg/dL Triglycerides >1000 mg/dL	Same as for grade 2.	Same as for grade 3.

**Prevention/Prophylaxis:**

Life-style modifications, as appropriate (balanced diet, limit alcohol consumption, increase physical activity)

ULN=upper limit of normal.

### 11.6.3 Management of Oral Mucositis

Guidance on TAK-228 dose modification for patients with oral mucositis is provided in Table 10.

**TABLE 10 MANAGEMENT OF ORAL MUCOSITIS**

Grade	Description	Treatment	Dose Modification
1	Asymptomatic or mild symptoms.	
 
Nonalcoholic mouth wash or 0.9% salt water rinse.
 
Consider topical corticosteroids at earliest signs of mucositis.
 
	None
2	Moderate pain, not interfering with oral intake. Modified diet indicated.	
 
Topical analgesic mouth treatments.
 
Topical corticosteroids.
 
Initiate antiviral or antifungal therapy, if indicated.
 
	
 
Maintain TAK-228 dose if tolerable.
 
Hold only TAK-228 if intolerable until recovery to <math>\leq</math>grade 1, then restart at same dose.
 

3	Severe pain, interfering with oral intake.	
 
Same as for grade 2.
 
Consider intralesional corticosteroids.
 
	
 
Hold TAK-228 until recovery to <math>\leq</math>grade 1, then restart TAK-228 at a dose reduced by 1 level.
 

4	Life-threatening consequences.	
 
Same as for grade 2.
 
Consider intralesional corticosteroids.
 
	
 
Stop TAK-228 and discontinue patient from the study.
 

**Prevention/Prophylaxis:**

- Initiation of a nonalcoholic mouth wash or 0.9% salt water rinses 4 to 6 times daily is strongly recommended at the start of therapy before signs of mucositis develop.
- Avoid using agents containing hydrogen peroxide, iodine, and thyme derivatives in management of stomatitis, as they may worsen mouth ulcers.

#### 11.6.4 Management of Rash

Guidance on TAK-228 dose modification for patients with rash is provided in Table 11.

**TABLE 11 MANAGEMENT OF RASH**

Grade	Description	Treatment	Dose Modification
$\leq$ 2	Macules/papules covering $\leq$ 30% body surface area with or without symptoms.	Consider treatment with topical steroid cream/ointment and/or oral anti-histamines or antibiotics.	None
$\geq$ 3	Macules/papules covering $>$ 30% body surface area with or without symptoms.	Consider treatment with topical steroid cream/ointment, oral anti-histamines, oral antibiotics, and/or pulsed steroids.	
 
Hold TAK-228 until <math>\leq</math>grade 2.
 
Resume TAK-228 based on timing of recovery: 
 
<math>\leq</math>3 weeks: reduce TAK-228 by 1 dose level.
 
<math>></math>3 weeks: stop TAK-228 and discontinue patient from the study.
 
 
 

Patients who develop grade 4 rash should permanently discontinue study treatment, unless they derive clinical benefit, in which case they may be retreated at a reduced dose level after recover to  $\leq$ grade 1 severity. Grade 4 rash is defined as rash acneiform/papulopustular with papules and/or pustules covering any % body surface area, which may or may not be associated with symptoms of pruritus or tenderness, and are associated with extensive superinfection with IV antibiotics indicated; life threatening consequences (NCI CTCAE Version 4.03, effective date 14 June 2010).

**Prevention/Prophylaxis:**

- Rash should be managed aggressively. The investigator should consider consulting a dermatologist or other specialist, if needed.
- A skin biopsy at the site of rash should be considered as soon as possible after the initial episode.

#### 11.6.5 Management of Nausea/Vomiting

Guidance on TAK-228 dose modification for patients with nausea and/or vomiting is provided in Table 12.

